5.7.1 Sample Collection Guidelines

Sampling Schedule

Blood sample for correlative studies will be collected at the following time points:

- Screening
- Day 1 of each cycle, pre-treatment and 1 hour after each UC-961 infusion.
- End of Treatment visit
- Response assessment
- Long-Term Follow-up visits

Sample Collection and Handling Instructions

Blood samples (approximately 15-20 ml) will be collected in anticoagulated (ACD) tubes at a site distant from the infusion for pharmacokinetic evaluation. Samples cannot be drawn from the 2nd lumen of a multi-lumen catheter through which drug is being administered. The exact time that the sample is drawn along with the exact time that the drug is administered should be recorded.

Sample Processing

Samples will be processed in the translational lab of [name], with separation of plasma, followed by isolation of mononuclear cells or neutrophils by Ficoll or Percoll differential centrifugation, respectively.

Sample Labeling

Each tube must be labeled with the patient's study number and the date and time the sample was drawn. Data should be recorded on the Correlative Study Form, which must accompany the sample(s).

5.7.2 Specimen Banking

Patient samples collected for this study will be retained at the UCSD School of Medicine ([name] Laboratory). Specimens will be stored indefinitely or until they are used up. If future use is denied or withdrawn by the patient, best efforts will be made to stop any additional studies and to destroy the specimens. Samples will be labeled with the subject's de-identified study number and collection date. The link between study number and medical record number will be viewed over a password secured encrypted server-client.

Drs. [name] will be responsible for reviewing and approving requests for research specimens from potential research collaborators outside of UCSD. Collaborators will be required to complete an agreement (a Material Transfer Agreement or recharge agreement) that states specimens will only be released for use in disclosed research. Any data obtained from the use of clinical specimens will be the property of UCSD for publication and any licensing agreement will be strictly adhered to.

The study research coordinator will review the subject's medical record for demographic and clinical information pertaining to the subject's general medical history, diagnosis, and outcomes of any treatments received. Samples and data extracted from the subject's medical record will be coded with a de-identified study number, and the subject's name and identifying information will be removed. A log that links the subject's name and identifiers to the study number will be maintained in a secure database distinct from the secure database into which the subject's clinical information will be entered

The specimens and their derivatives may have significant therapeutic or commercial value. The Informed Consent form contains this information and informs the subject that there is the potential for financial gain by UCSD, the investigator or a collaborating researcher or entity.

The following information obtained from the subject's medical record may be provided to research collaborators when specimens are made available:

- Diagnosis
- Collection time in relation to study treatment
- Clinical outcome if available
- Demographic data

6.0 Schedule of Events

Treatment Cycle	Screening	Extension Course 1	Response Assessment 1	Extension Course 2	Response Assessment 2	Long-Term Follow-up
Visit Day		1, 15, 29, 43, 57, 85, 113, 141	169 ⁶	197, 211, 225, 239, 253, 281, 309, 337 ⁷	365 ⁶	Q28d x8, then q56d
Visit window	≤ 30 days prior to visit 2	±3d	±7d	±3d	±7d	±7d
Informed Consent	X					
Eligibility Checklist	Х					
History and Symptoms	Х	Х	Х	Х	X	Х
VS/Ht and Wt	Х	Х	Х	Х	X	Х
Comprehensive PE	Х	Х	X	Х	X	Х
ECOG Performance Status	X	Х	Х	Х	Х	Х
CBC and differential	×	X	X	X	X	X
Blood chemistry panel ¹	Х	Х	Х	Х	Х	Х
ECG	Х					
Adverse Events Screen		Х	Х	Х	Х	Х
Concomitant Medication		Х	X	Х	X	Х
UC-961 Administration		Х		X		
CT scan Chest/ Abdomen/ Pelvis ²	within 60 days of C1D1		Х		Х	
Bone marrow aspirate and biopsy ³	within 90 days of C1D1		Х		Х	
Cytogenetics/FISH from bone marrow or peripheral blood ⁴	X		×		Х	
Serum hCG for female	within 14 days of C1D1					
of child bearing potential Quantitative T-cell subsets	X		Х		Х	

Treatment Cycle	Screening	Extension Course 1	Response Assessment 1	Extension Course 2	Response Assessment 2	Long-Term Follow-up
Visit Day		1, 15, 29, 43, 57, 85, 113, 141	169 ⁶	197, 211, 225, 239, 253, 281, 309, 337 ⁷	365 ⁶	Q28d x8, then q56d
Visit window	≤ 30 days prior to visit 2	±3d	±7d	±3d	±7d	±7d
PT/aPTT	X					
Collection of Pharmacokinetic and Pharmacodynamic Samples ⁵	Х	Х	PD only	Х	PD only	PD only

- 1. Chemistry panel to include: comprehensive metabolic panel (Na+, Cl-, K+, CO2, BUN, Creatinine, Glucose, Ca2+, total protein, albumin, total bilirubin, SGPT, SGOT, alkaline phosphatase), phosphorous, magnesium, uric acid, LDH, amylase, and lipase. NOTE: amylase and lipase are not measured in long-term follow-up unless clinically indicated.
- 2. Or MRI or PET scan.
- 3. In the case of a CR, an additional bone marrow will be taken two months after patient first achieves CR
- 4. Chromosome analysis and FISH Panel to include 11q, 12p, 13q, 17p analysis.
- 5. Blood samples are collected for PK and/or PD analysis (refer to section 5.8 and 5.9)
- 6. May be done earlier if progressive disease is suspected.
- 7. Or 28 days after Response Assessment 1.

7.1 Safety/tolerability

7.1.1 Common Terminology Criteria for Adverse Events (CTCAE)

Analyses will be performed for all patients having received at least one dose of study drug. The study will use the CTCAE version 4.03 (http://ctep.cancer.gov/reporting/ctc.html) for reporting of non-hematologic adverse events.

7.1.2 International Working group for Chronic Lymphocytic Leukemia (IWCLL) criteria for hematologic toxicity

As is the case with virtually all of the hematological malignancies, an evaluation of the hematological toxicity in patients with CLL must consider the high frequency of marrow involvement and consequent medullar compromise at the initiation of therapy. A substantial proportion of patients will have hematological parameters within the range of Grade 2-4 hematological toxicity before therapy is given; therefore, a modified schema will be used to monitor hematological toxicity in patients with CLL. The modified hematological toxicity schema is displayed:

Modified Grading Scale for Hematological Toxicity in CLL Studies			
Grade ¹	Decrease in platelets (nadir) from pretreatment value (%) ²	ANC/μI (nadir)³	Hemoglobin ⁴
0 (not AE)	10%, or above lower limit of normal for institution.	≥ 1800, or above lower limit of normal for institution.	Baseline or higher, or above lower limit of normal for institution.
1	11-24%	≥ 1500 and < 1800	> 10.0 g/dL and below baseline
2	25-49%	≥ 1000 and < 1500	< 10.0 – 8.0 g/dL and less than baseline
3	50-74%	≥ 500 and < 1000	< 8.0 – 6.5 g/dL and less than baseline
4	≥75% or ≤ 25,000/mm3 ²	< 500	< 6.5 g/dL and less than baseline

^{*}This schema concurs with the CTEP CTCAE 4.03, except for the platelet values are taken from the iwCLL-WG guidelines working group criteria and hemoglobin toxicity modified from CTCAE only to account for low baseline values in CLL patients. No hematologic toxicity will be registered unless hemoglobin falls below baseline level.

¹ Grades: 1, mild; 2, moderate; 3, severe; 4, life threatening; 5, fatal. Death occurring as a result of toxicity at any level of decrease from pretreatment will be recorded as a Grade 5.

² Treatment will be held for platelet count ≤ 25,000/mm3, even if it does not meet grade 4 criteria based on percent decrease. See section 4.6.1 for dose hold/adjustment guidelines.

³ If baseline ANC is <1,500/μL, neutrophil toxicity cannot be evaluated. In that case, if

the neutrophil count is less than $500/\mu L$, it is still recommended to hold therapy until ANC is greater than $500/\mu L$.

⁴ If baseline Hemoglobin is < 10.0, hemoglobin toxicity cannot be evaluated. In that case, if the hemoglobin is less than 6.5, it is still recommended to hold therapy until Hgb is greater than 6.5.

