3.0 PATIENT ELIGIBILITY

3.1 Inclusion Criteria

Subjects must meet all of the inclusion criteria to participate in this study.

- **1.** Ability to understand and the willingness to sign a written informed consent.
- 2. Clinical and phenotypic verification of B cell CLL and measurable disease. Immunophenotyping of the leukemic cells (blood or marrow) must demonstrate a monoclonal (or light chain positive) B cell population with immunophenotype consistent with CLL (e.g., co-expressing CD19 and CD5).
- **3.** Recovered from toxic effects attributed to UC-961 to grade 1 levels, or baseline.
- **4.** Must have measurable disease, including one of the following: absolute lymphocyte count greater than 5000/uL, lymphadenopathy greater than 1.5cm in longest dimension, splenomegaly (palpable at least 1 cm below the costal margin or radiographically enlarged), bone marrow biopsy with residual CLL cells, or resultant bone marrow dysfunction (platelet count < 100k /uL, hemoglobin < 10 g/dL).
- **5.** Women of childbearing potential (not postmenopausal for at least one year or not surgically incapable of bearing children) must agree not to become pregnant for the duration of the study. Both men and women must agree to use a barrier method of contraception for the duration of the study and until 10 weeks after the final dose of UC-961 (expected to be greater than 5 half-lives from pre-clinical data).
- **6.** Subjects must have an ECOG performance status of 0-2.
- **7.** Adequate hematologic function:
 - Platelet count ≥ 50,000/µL unless due to heavily infiltrated bone marrow (> 80% CLL cell infiltrate); AND
 - Hemoglobin ≥ 8.0 g/dL (may be supported by erythropoietin); AND
 - Absolute neutrophil count > 1000 /uL unless due to heavily infiltrated bone marrow (> 80% CLL cell infiltrate).
- 8. Adequate renal function:
 - Serum creatinine <1.5 times upper limit of normal; OR
 - Calculated Creatinine clearance (CrCl) ≥ 40 mL/min (based upon the Cockcroft-Gault Equation [CrCl = (140-age) * actual wt (in kg) * (0.85 if female) / (72 * Cr)].
- **9.** Adequate hepatic function:
 - Total bilirubin ≤ 2.5 times upper limit of normal; AND
 - ALT ≤ 2.5 times upper limit of normal.
- **10.** Adequate coagulation tests:
 - Prothrombin time international normalized ratio (INR) ≤ 2; AND
 - Partial thromboplastin time ≤ 1.66 times upper limit of normal.

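### Section 7.1.2 platelet grading: the absolute Grade 4 criterion has no baseline condition, so a patient who enters at or below 25,000/mm3 is Grade 4 without a meaningful fall

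*Combined protocol and SAP*

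**What the plan says.** Section 7.1.2 gives its reason for departing from standard grading: "A substantial proportion of patients will have hematological parameters within the range of Grade 2-4 hematological toxicity before therapy is given". The platelet column is headed "Decrease in platelets (nadir) from pretreatment value" and uses percent bands: Grade 1 from 11 to 24%, Grade 2 from 25 to 49%, Grade 3 from 50 to 74%. Grade 0, which the table labels as not an adverse event, is printed as 10% or above the institution's lower limit of normal. The Grade 4 cell is "≥75% or ≤ 25,000/mm3".

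The other two lineages are handled differently. The Grade 4 hemoglobin cell in the same row is "< 6.5 g/dL and less than baseline". Footnote 3 says that with a baseline ANC under 1,500/µL "neutrophil toxicity cannot be evaluated". Footnote 4 says "If baseline Hemoglobin is < 10.0, hemoglobin toxicity cannot be evaluated". The platelet footnote, number 2, concerns holding treatment at or below 25,000/mm3, "even if it does not meet grade 4 criteria based on percent decrease".

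On entry, Section 3.1 item 7 asks for platelets of at least 50,000/µL, "unless due to heavily infiltrated bone marrow (> 80% CLL cell infiltrate); AND". No lower limit is attached to that exception.

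**The concern.** The scale is meant to keep cytopenia that was present before treatment from being recorded as toxicity. The percent bands do this for platelets, and the below-baseline wording and footnotes 3 and 4 do it for hemoglobin and ANC. The absolute platelet criterion does not. A patient admitted under the marrow exception at or below 25,000/mm3 meets it before the first dose and goes on meeting it at every blood count, even if nothing changes.

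The recorded grade is at stake, not the patient's management. Section 10 reports adverse event incidence in a study whose primary aim is safety, and the six-monthly DSMB report in Section 11.4 covers every adverse event whatever its grade or attribution. One assessor may record a life-threatening platelet event for a count that another records as no event.

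**Working it through.** The plan gives no figure to reproduce. The check applies the platelet column as written to example counts.

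**Inputs.** The bands and the 25,000/mm3 criterion come from Section 7.1.2. The Grade 0 cell prints 10% without an operator; it is read here as up to 10%, because Grade 1 starts at 11%. The patient numbers, 33 anticipated and up to 75, come from the synopsis. The counts are illustrations, not trial data.

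**Formula.** Percent decrease = 100 × (baseline − nadir) / baseline.

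| Baseline → nadir | Percent decrease | Grade by percent | Meets ≤25,000 (Grade 4)? | Grade under the proposed footnote |
|---|---|---|---|---|
| 24,000 → 24,000 | 0/24 = 0% | 0 | yes | 0 |
| 20,000 → 19,000 | 1/20 = 5.0% | 0 | yes | 0 |
| 24,000 → 22,000 | 2/24 = 8.3% | 0 | yes | 0 |
| 20,000 → 22,000 (a rise) | −2/20 = −10% | 0 | yes | 0 |
| 20,000 → 14,000 | 6/20 = 30% | 2 | yes | 2 |
| 24,000 → 8,000 | 16/24 = 66.7% | 3 | yes | 3 |
| 20,000 → 5,000 | 15/20 = 75% | 4 | yes | 4 |
| 26,000 → 25,000 | 1/26 = 3.8% | 0 | yes | 4 (kept) |
| 80,000 → 24,000 | 56/80 = 70% | 3 | yes | 4 (kept) |

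In the first four rows the patient has not worsened materially, yet the absolute criterion makes the count Grade 4.

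**Does other text remove the problem?**
- Footnote 2 says when to hold treatment. It does not cancel the absolute criterion, which stands in the Grade 4 cell in its own right.
- The note to Section 4.6.1 applies holds and dose adjustments even when heavy marrow infiltration puts baseline values below the thresholds. It shows that such patients are foreseen, but it governs dosing, not grading.
- The note under the 7.1.2 table that requires a fall below baseline names hemoglobin only. Even if it were extended to platelets, it would cover 24,000 → 24,000 but not 20,000 → 19,000.
- Section 8.0 lets an abnormal laboratory finding be an adverse event, so the general definition does not clearly exclude a persistently low count.

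**Size.** The number of entrants at or below 25,000 is not given. Assuming 0, 1 or 2, all graded by the absolute criterion, the Grade 4 incidence shifts by:
- n = 33: 0; 1/33 = 3.0 points; 2/33 = 6.1 points.
- n = 75: 0; 1/75 = 1.3 points; 2/75 = 2.7 points.

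**Route to the DLT rate.** Section 4.2 counts Grade 4 hematologic toxicity only if it is at least possibly related and falls within 28 days of starting treatment. The phase 1 experience reported before Section 1.4 attributes all hematologic adverse events to the underlying disease. For an unchanged count the expected shift in the DLT rate is therefore at or near zero.

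**The case against.** The best defense is that a sensible assessor would choose Grade 0. The column heading speaks of a decrease, an unchanged count is not one, Grade 0 is labelled as not an adverse event, and the section exists to allow for low starting counts. Section 10 also lists adverse events with their relationship to treatment, so a pre-existing cytopenia would appear with its attribution, and the analysis is descriptive. This stands as a reason to expect little harm. It does not settle the grade: the 25,000 criterion is an absolute count joined by an or, and a fall of 5.0% is a decrease.

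A second objection is that an absolute threshold for a dangerous platelet count is a legitimate conservative choice. That is accepted for anyone who starts above 25,000. A reader might infer that every count matching two rows is an error because the table names no winning row. That goes too far. A cell combining a percent and an absolute criterion will always overlap other rows, and calling 80,000 → 24,000 Grade 4 despite its 70% fall is reasonable. The defect is only the missing baseline condition.

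A third objection is that baselines just above 25,000 behave alike: up to 25,000/0.9, about 27,778, a fall of 10% or less reaches the threshold. That is true, and any cutoff has such an edge. These patients have at least crossed the threshold on treatment, so Grade 4 is defensible provided the footnote says so.

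**Conclusion.** The gap is real but minor. For patients entering at or below 25,000/mm3, the Grade 4 platelet cell can label a stable pre-existing count as Grade 4, against the section's stated purpose and unlike ANC and hemoglobin. The effect is on Grade 4 adverse event incidence and the DSMB summary: 3.0 points per affected patient at 33 patients, 1.3 at 75.

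This rests on reading the Grade 0 cell as up to 10% for the small-fall examples (the unchanged count does not depend on it) and on at least one such patient enrolling. The documents do not say how many will; the number is probably very small and may be zero. The phase 1 table shows thrombocytopenia only at Grade 1 (4 patients) and Grade 2 (1 patient), but the grading scale behind it is not shown.

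A reader might infer that the DLT rate named as primary endpoint is inflated, or that enrollment could be halted. The documents do not support either. A DLT needs attribution to the drug, the Section 4.9 stopping rule counts deaths and non-hematologic Grade 4 events, and Section 10 sets no DLT threshold.

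**What to change.** Add a platelet footnote to the 7.1.2 table with three parts:

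1. If the baseline platelet count is at or below 25,000/mm3, the absolute criterion does not define Grade 4, and platelet toxicity is graded by percent decrease from baseline only.
2. If baseline is above 25,000/mm3, a fall to 25,000 or below remains Grade 4, including a fall from 26,000 to 25,000.
3. The hold at or below 25,000/mm3 and the Section 4.6.1 rules are unchanged.

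The cost is one footnote. Blood counts are already taken at screening and at every infusion, so no new data are needed.

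The downside is that some real falls from a very low baseline receive a lower grade. A fall from 24,000 to 8,000 (66.7%) becomes Grade 3 and is handled by the hold rather than being a potential DLT; Grade 4 from 24,000 would need 24,000 × 0.25 = 6,000 or less. The rule is still stricter than footnotes 3 and 4, which do not grade low-baseline ANC or hemoglobin at all. Adding only a below-baseline condition, as for hemoglobin, would avoid this loss but leave 20,000 → 19,000 at Grade 4.

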4.2 Dose Limiting Toxicity

Dose-Limiting Toxicity (DLT) is defined as any of the following adverse events that are considered by the investigator to be possibly, probably, or definitely related to the study agent UC-961 within the 28 days of the start investigational treatment:

- CTCAE Grade 3 or higher non-hematologic toxicity, except for: Grade 3 infections lasting < 7 days that have resolved, or one occurrence of Grade 3 infusion reaction; or
- Grade 4 or higher hematologic toxicity (by modified iwCLL criteria); or
- Any AE requiring a dose delay of greater than 28 days;

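### The 4.6.1 hemoglobin hold has no hemoglobin level for release, and the 7.1.2 note says hematologic where it should say hemoglobin

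*Combined protocol and SAP*

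**What the plan says.** **Dosing.** The hematologic row of Section 4.6.1 starts a hold on any of three findings: ANC below 500, hemoglobin below 6.5 g/dL, or a platelet fall of at least 75% (and/or a count of 25,000 or less). The first- and second-occurrence entries carry the same release condition: ANC at least 500 and platelets at least 25,000. Neither mentions hemoglobin.

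**Grading.** The table in Section 7.1.2 grades platelets, ANC and hemoglobin in separate columns. Grade 4 hemoglobin is "< 6.5 g/dL and less than baseline". The note below the table says "No hematologic toxicity will be registered unless hemoglobin falls below baseline level". Footnote 4, attached to the hemoglobin column, says "If baseline Hemoglobin is < 10.0, hemoglobin toxicity cannot be evaluated". It adds that if such a patient drops below 6.5, "it is still recommended to hold therapy until Hgb is greater than 6.5".

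**Eligibility.** Section 3.1 admits patients with hemoglobin from 8.0 g/dL. Among the findings that count as measurable disease it lists "resultant bone marrow dysfunction (platelet count < 100k /uL, hemoglobin < 10 g/dL".

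**Use of the scale.** Section 8.2 grades all hematologic adverse events on it. Two of the DLT routes in Section 4.2 matter here: "Grade 4 or higher hematologic toxicity (by modified iwCLL criteria); or" and "Any AE requiring a dose delay of greater than 28 days". Section 10 names the DLT rate as the primary endpoint.

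**The concern.** A hold rule needs an end that matches its cause. Here one of the three causes is missing from the release line, so a clinician who follows 4.6.1 to the letter could redose a patient whose hemoglobin is still below 6.5 g/dL.

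The note raises a different problem. It sits in the scale that defines a hematologic DLT. As worded it makes a hemoglobin fall a precondition for recording toxicity in any cell line, which overrides two of the three columns. Two people applying the text to the same blood counts could reach different DLT counts.

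Footnote 4 raises a smaller question. It takes a group that the eligibility criteria expressly expect out of the Grade 4 hemoglobin route, and the plan does not say how the DLT rate will show this.

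**Working it through.** No sample size or power figure bears on this point, so the check is whether the rules agree with one another.

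**1. Trigger against release (4.6.1).**

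- Trigger = ANC < 500, or Hgb < 6.5, or platelets down ≥ 75%, or platelets ≤ 25,000.
- Release = ANC ≥ 500 and platelets ≥ 25,000.

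If hemoglobin is the only trigger, ANC is not below 500 and platelets are not at or below 25,000. Both release conditions are then already true. This holds for every hemoglobin-only hold. Example: Hgb 6.0, ANC 2,000, platelets 150,000 with no platelet fall. The trigger is met and so is the release.

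**2. Who is protected by other rules.**

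| Rule | Covers | Does not cover |
|---|---|---|
| 4.5, criteria for dosing | Ongoing Grade 4 hematologic toxicity attributable to UC-961 | Events not attributed to the drug; hemoglobin events left ungraded by footnote 4 |
| 4.2 with 4.6, DLT ends treatment | At least possibly related, first 28 days | Events judged unlikely related, at any time |
| 4.6.1, autoimmune row | Autoimmune anemia, held until Grade 1 or less | Other causes |
| 7.1.2, footnote 4 | Baseline below 10.0: hold recommended until Hgb exceeds 6.5 | Baseline 10.0 or more |

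Section 4.6 exempts only events that are definitely unrelated, and Section 8.4 has a separate category for unlikely. An unlikely-related event therefore starts the hold but is outside the DLT rule. It is also outside 4.5 if attributable there means at least possibly related, which is an assumption because 4.5 does not define the word. The gap is mainly baseline Hgb ≥ 10.0, not autoimmune, judged unlikely related.

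**3. The note, read literally (7.1.2).** Hemoglobin unchanged in both examples:

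- ANC from 2,000 to 300: below 500, so Grade 4 by its column.
- Platelets from 150,000 to 20,000: fall = 130,000/150,000 = 86.7%, so Grade 4 by percentage and by count.

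By the columns, either event is a DLT if at least possibly related and within the first 28 days. By the literal note, neither is registered.

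**4. Footnote 4 against the hemoglobin column.** From a baseline of 10.0 or more, any value below 10.0 is already below baseline, so the below-baseline condition in Grades 2 to 4 excludes nothing. On a 0.1 g/dL grid from 4.0 to 16.0 it excludes 0 value pairs for baselines of 10.0 or more. For baselines 8.0 to 9.9 it excludes 20 + 19 + … + 1 = 210. The condition has work to do only in the group that footnote 4 removes.

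| Baseline | Nadir | Grade by column | Under footnote 4 |
|---|---|---|---|
| 9.5 | 9.0 | 2 | not evaluable |
| 9.5 | 7.5 | 3 | not evaluable |
| 9.5 | 6.0 | 4 | not evaluable |
| 8.0 | 7.9 | 3 | not evaluable |
| 8.0 | 6.4 | 4 | not evaluable |
| 12.0 | 6.0 | 4 | 4 |

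Reaching Grade 4 takes a fall of more than 8.0 − 6.5 = 1.5 g/dL (18.75%) from 8.0, 2.5 (27.8%) from 9.0, 3.4 (34.3%) from 9.9 and 3.5 (35.0%) from 10.0. A related fall to 6.0 in the first 28 days that recovers within 28 days is a DLT from 10.0. From 9.9 it is not; only the delay route remains.

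**5. Known frequency.** The phase 1 adverse event table just before Section 1.4 lists anemia, thrombocytopenia and neutropenia. Grade 1: 6 + 4 + 3 = 13. Grade 2: 0 + 1 + 1 = 2. Total 15, none at Grade 3 or 4.

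**The case against.** **The note is a typing slip.** The clause before it concerns hemoglobin, and footnotes 2 and 3 give platelets and ANC their own hold rules with no reference to hemoglobin. This stands. A reader might infer that the trial would really leave severe platelet or neutrophil falls unrecorded; the surrounding text does not support that. The sentence still needs correcting because it sits in the scale behind the DLT rate.

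**The release gap is narrow.** Besides the rules tabulated above, Note 1 to 4.6.1 requires re-assessment within 7 days, 4.7 allows blood products for Grade 4 toxicity, and 4.9 lets the physician stop the drug. This stands too. A reader might infer that the plan generally allows redosing through severe anemia; it does not. Nor can the gap be sized by counting doses given after the 28-day DLT window, because the DLT rule never covers an unlikely-related event, whatever the day. What remains is that none of these provisions puts a hemoglobin level into the release lines.

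**Footnote 4 is an exception, not a contradiction.** It is attached to the column heading and parallels footnote 3, which does the same for a low baseline ANC. The below-baseline condition does real work in Grade 1, so its repetition in Grades 2 to 4 may be parallel drafting. This is largely right: redundancy shows loose drafting, not two rules that cannot both apply. Nor do hemoglobin falls in these patients vanish from the safety data. Section 8.2 has a general severity scale for events without a grade, Section 10 summarizes laboratory abnormalities, and the DSMB receives all adverse events. What remains is the Grade 4 DLT route, which 4.2 ties to the modified scale.

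**Conclusion.** Two statements are wrong as written. The 4.6.1 release lines omit one of the hold's own triggers, so every hemoglobin-only hold meets release at onset. The 7.1.2 note, taken literally, overrides the platelet and ANC columns. Both follow from the text without assumptions. Confining the first to unlikely-related events with baseline 10.0 g/dL or more rests on reading attributable in 4.5 as at least possibly related; a wider reading would shrink the gap further.

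Footnote 4 is a secondary matter for the sponsor to decide. Its effect is that eligible patients with baseline 8.0 to below 10.0 g/dL cannot have a hemoglobin DLT by the Grade 4 route. The documents do not give the share of such patients, so the effect on the DLT rate cannot be computed.

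The 4.6.1 platelet release level might also look mismatched to its percentage trigger. The right recovery level is a clinical choice, and this point makes no claim about it.

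The priority is minor to should-fix. The affected group is narrow and nothing in the phase 1 table reached these grades, but the errors touch a dosing rule and the endpoint that Section 10 calls primary.

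**What to change.** 1. **Section 4.6.1:** add a hemoglobin condition to both the first- and second-occurrence release lines, for example hemoglobin ≥ 6.5 g/dL. Footnote 4 releases only above 6.5, so choose one form and use it in both places. Cost: slightly longer holds. A few more patients may reach the 28-day delay limit in Note 2 and be discontinued.

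2. **Section 7.1.2 note:** replace the word hematologic with hemoglobin. Cost: none beyond the edit.

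3. **Footnote 4, sponsor's choice:** either
   - keep it, and report beside the DLT rate how many patients were not evaluable for hemoglobin and how many for ANC (footnote 3); or
   - grade Grade 4 hemoglobin falls in patients with baseline below 10.0.

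   The first option costs two counts from blood counts already collected. Under the second, a low-baseline patient with a related fall below 6.5 in the first 28 days would have a DLT and stop treatment. Limiting it to Grade 4 avoids calling a drift from 8.0 to 7.9 Grade 3, which full use of the column would do. Under either option the hold for these patients should stay.

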4.6 Dose Modifications and Dosing Delays

Each patient will be assessed for the development of toxicity according to the NCI Common Toxicity Criteria for Adverse Events (CTCAE), version 4.03 for non-hematologic toxicity or modified iwCLL criteria (section 7.1.2) for hematologic toxicity. Patients experiencing a DLT as defined in section 4.2 will be discontinued from study treatment. Otherwise, dose adjustments should be made according to the system showing the greatest degree of toxicity, as per 4.6.1, unless the adverse event is definitely unrelated to the study drug. Dose levels are listed in section 1.4.

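### Section 7.1.2 gives two answers on hemoglobin when baseline is below 10.0 g/dL; if footnote 4 is followed, a related fall below 6.5 g/dL can be missing from the DLT rate

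*Combined protocol and SAP*

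**What the plan says.** **Grading (Section 7.1.2).** The hemoglobin column defines Grade 4 as "< 6.5 g/dL and less than baseline", with no minimum baseline. Grades 2 and 3 carry the same baseline condition. The note under the table explains that the hemoglobin scale departs from CTCAE solely to allow for low starting values, and adds: "No hematologic toxicity will be registered unless hemoglobin falls below baseline level". Footnote 4, attached to the same column, says "If baseline Hemoglobin is < 10.0, hemoglobin toxicity cannot be evaluated" and recommends holding treatment below 6.5 g/dL.

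**Eligibility (Section 3.1).** Criterion 7 requires "Hemoglobin ≥ 8.0 g/dL (may be supported by erythropoietin". Criterion 4 lists "resultant bone marrow dysfunction (platelet count < 100k /uL, hemoglobin < 10 g/dL" among the ways to have measurable disease. Baselines of 8.0 to below 10.0 g/dL are therefore admitted.

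**Consequences.** Section 4.2 counts "Grade 4 or higher hematologic toxicity (by modified iwCLL criteria" as a DLT if it is at least possibly related and falls within 28 days of starting treatment. Section 4.6 adds: "Patients experiencing a DLT as defined in section 4.2 will be discontinued from study treatment". Section 10 names the DLT rate as the primary endpoint and treats everyone given one dose as evaluable for safety.

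**The concern.** The table and its note handle a low baseline by grading against it. Footnote 4 handles the same patients by not grading them. The plan does not say which rule prevails, or what follows for DLT status if the footnote does.

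Two things depend on the answer. One is whether a patient with a related fall below 6.5 g/dL in the first 28 days stops treatment or may be re-dosed. The other is whether that event enters the primary endpoint as Section 10 defines it. If the footnote is followed, a patient who starts below 10.0 g/dL cannot have a DLT through the hemoglobin grade, however far the value falls, although such patients start closest to 6.5.

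**Working it through.** The plan gives no figure to reproduce here. The check compares the rules, then sizes one event.

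**1. Does the baseline condition do any work if footnote 4 governs?** In Grades 2 to 4 the condition matters only when the on-study value is below 10.0 g/dL and also at or above baseline.
- Baseline 10.0 or higher: a value below 10.0 is always below baseline, so there are 0 such cases.
- Baseline 8.0 to 9.9 in steps of 0.1: baseline 8.0 allows 20 such values (8.0 to 9.9), 8.1 allows 19, and so on down to 1 at 9.9. The sum is 20 + 19 + … + 1 = 210.

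The condition has effect only for the patients whom footnote 4 removes. If the footnote governs, those words in Grades 2 to 4 are empty.

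**2. The same event under each rule.** Take a baseline of 9.0 g/dL and a value of 6.2 at the Day 15 visit, at least possibly related.

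| | Table | Footnote 4 |
|---|---|---|
| Grade in 7.1.2 | 4 (6.2 < 6.5 and 6.2 < 9.0) | none |
| DLT under 4.2, hematologic criterion | yes | no |
| Treatment | discontinued (4.6) | held; same dose on a first occurrence (4.6.1) |
| Contribution to the DLT rate | 1 | 0 |

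The severity scale in 8.2 for ungraded events cannot supply the DLT, because 4.2 requires the grade to come from the modified iwCLL scale. The remaining route in 4.2 is a dose delay of more than 28 days.

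**3. At the boundary.** A fall from 10.1 to 6.2 (3.9 g/dL) is Grade 4 under both rules. A fall from 9.9 to 6.2 (3.7 g/dL) is Grade 4 by the table and ungraded by the footnote.

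**4. Effect of one event on the DLT rate.** The input is N = 33, the enrollment anticipated in the synopsis. Exact (Clopper-Pearson) 95% intervals:
- 0/33: upper limit = 1 − 0.025^(1/33) = 10.6%.
- 1/33 = 3.0%, interval 0.1% to 15.8%.

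**5. How often?** The documents give neither the share of patients with baseline below 10.0 nor the risk of a related fall below 6.5. As a pure assumption, let k = 3 to 13 of 33 patients start low, with a risk p of 2% to 5% each.
- Expected events k × p: 3 × 0.02 = 0.06 to 13 × 0.05 = 0.65.
- Chance of at least one, 1 − (1 − p)^k: 1 − 0.98^3 = 6% to 1 − 0.95^13 = 49%.

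Nothing in the plan supports these values of p. The phase 1 safety summary before Section 1.4 points lower: six anemias, all Grade 1, with every hematologic event attributed to the disease.

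**The case against.** The best defense is that footnote 4 is a deliberate exception. It is tied to the hemoglobin column, it mirrors footnote 3 for neutrophils (baseline below 1,500/µL), and a specific note normally limits a general table. On that view some words in the table are redundant, but there is no contradiction. The parallel is imperfect. The neutrophil column has no baseline condition, so footnote 3 fills a gap, whereas the hemoglobin column already has one and footnote 4 cancels it. Even read as an exception, the footnote leaves DLT status unstated, and step 2 still follows.

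Much of the rest of the defense stands:
- Holds are covered. The hematologic row of 4.6.1 is triggered by the hemoglobin value itself, and footnote 4 recommends a hold.
- After the 28-day window, 4.6.1 allows restart at the same dose on a first occurrence at any baseline.
- The event would not disappear from the safety report. Section 8.2 gives it a severity, and Section 10 summarizes laboratory abnormalities separately.
- The neutrophil footnote raises the same DLT question, since entry requires only an ANC above 1,000/µL. Settling hemoglobin alone would leave that open.

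**Conclusion.** The conflict is real and worth correcting before an event has to be adjudicated. Its reach is narrow: a related fall below 6.5 g/dL, in the first 28 days, in a patient with baseline below 10.0. Each such event moves the DLT rate by 1/33, or 3.0 percentage points, at the anticipated enrollment. The expected number is small and cannot be derived from the documents. The analysis is descriptive, and no threshold depends on the result.

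A reader might infer more in three ways, none of which the documents support:
- *Low-baseline patients should leave the DLT denominator.* They can still have a non-hematologic, platelet, neutrophil or delay DLT, so counting them in the overall rate is right. Upper limits on a reduced denominator would describe a hemoglobin-only rate that the plan never defines.
- *Most of the trial is affected.* The sentence "A substantial proportion of patients will have hematological parameters within the range of Grade 2-4 hematological toxicity before therapy is given" concerns blood counts in general, not hemoglobin below 10.0.
- *The 8.0 g/dL entry floor guarantees a fall of at least 1.5 g/dL before Grade 4.* The plan does not define baseline. Screening may precede Day 1 by up to 30 days, and the CBC is repeated on Day 1, so a Day 1 baseline could lie below 8.0.

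**What to change.** 1. Replace footnote 4 in Section 7.1.2 with: *If baseline hemoglobin (last value before the first extension dose) is <10.0 g/dL, a fall to <6.5 g/dL and below baseline is Grade 4 and counts under 4.2 if at least possibly related; hold until hemoglobin is >6.5 g/dL.* The 28-day window in 4.2 applies unchanged. Keep the hold level in the footnote, because the recovery rule in 4.6.1 names only neutrophils and platelets.
2. State in 4.2 whether footnote 3 (baseline ANC <1,500/µL) precludes a neutrophil DLT.
3. In Section 10, report the number of patients with baseline hemoglobin <10.0 g/dL beside the DLT rate, and keep them in the denominator.

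The cost is a few lines of text and no new data, since a CBC is already taken at every infusion visit. There are two trade-offs. A few low-baseline patients with a related fall below 6.5 g/dL in the first 28 days will stop treatment, as patients with baseline 10.0 or higher already do. With the not-evaluable wording gone, Grades 2 and 3 follow the table as written, so a small drop such as 9.0 to 8.9 g/dL is listed as Grade 2; that does not make it a hematologic DLT.
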